6. STUDY OBJECTIVES AND PURPOSE

6.1. Primary Objectives

[figure not shown]
The primary objective is to assess the long-term safety and tolerability of the OCA + BZF FDC tablet in subjects with PBC.

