7.6. Dosage Adjustment Criteria

Dose frequency may be modified for the management of pruritus as described in [Section 14.1.3.1](#). In the event of tolerability issues such as pruritus, the dosing frequency may be decreased at the discretion of the Investigator.

Subjects can be discontinued from investigational product by the Investigator at any time for clinical safety concerns. Subjects who are discontinued from investigational product should be requested to continue with study visits until Month 60/end of study (EOS). Subjects who discontinue investigational product may be requested to come in for an Unscheduled Visit at the discretion of the Investigator depending on the timing of their next scheduled study visit.

Refer to [Section 8.4.1](#) for guidance on mandatory discontinuation of investigational product due to severe and related AEs. Refer to [Section 8.4.2](#) for other reasons of discontinuation of investigational product (e.g., withdrawal of consent, lost to follow-up, or pregnancy).

Subjects who were taking UDCA should continue this as a concomitant medication for the entirety of the study unless there is a tolerance or safety event related to UDCA that would require discontinuation.

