14.1.3.1. Severity of Pruritus (as an Adverse Event)

To ensure consistency in reporting, pruritus AEs must be graded for severity (i.e., intensity). As pruritus is a subjective symptom, clinical judgment should be used to determine its severity and management, as shown in Table 10. In order to assess the potential improvement in pruritus with treatment, baseline pruritus presence (yes/no) and severity (as shown in Table 10) will be determined.

Table 10: Severity of Pruritus

Pruritus Grade	Clinical Description of Severity for Pruritus and Medical Intervention
1=Mild	Mild or localized; topical intervention indicated
2=Moderate	Intense or widespread; intermittent; skin changes from scratching (e.g., edema, papulation, excoriations, lichenification, oozing/crusts); oral intervention indicated; limiting instrumental activities of daily living
3=Severe	Intense or widespread; constant; limiting self-care activities of daily living or sleep; oral corticosteroid or immunosuppressive therapy indicated

Since pruritus is a subjective symptom and the occurrence and magnitude of which are not readily measured by objective tools, clinical judgment needs to be applied in the management of each subject. Managing OCA-related pruritus may help improve tolerance in those subjects who experience problematic pruritus and may otherwise discontinue from the study prematurely. General guidance for the management of subjects experiencing significant pruritus includes the following:

- Drug holiday: A drug holiday is defined as an Investigator's "prescribed" complete interruption of dosing for 1 or more consecutive days (i.e., nondaily dosing does not constitute a drug holiday). Details of drug holidays and/or nondaily dosing regimens should be recorded in the eCRF. If the drug holiday lasts more than 30 days, the subject should be permanently discontinued from investigational product but requested to continue with study visits until Month 60/EOS.
- Per [Section 8.4.1.1](#), subjects with pruritus \geq Grade 3 in severity and possibly, probably, or definitely related to the investigational product must discontinue investigational product but are encouraged to continue study visits.

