- Subjects taking BAS (including cholestyramine and its derivatives, colestipol, colesevelam, or other BAS) or aluminum hydroxide- or smectite-containing antacids should refrain from using these drugs for the management of pruritus during the trial. The use of BAS may alter the interpretation of the effects of BZF on pruritus.
- Other therapies may be tried as deemed clinically appropriate.
- Rifampin should be used with caution in patients with PBC due to the hepatotoxicity concerns as specified in the rifampin USPI.
- Less frequent dosing of investigational product (e.g., on alternate days) may be administered, after which, subjects may return to their original daily dose as soon as tolerated.

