15.3.1. Adverse Events

AEs will be coded using the Medical Dictionary of Regulatory Activities (MedDRA). Summary tables of TEAEs will be provided. The incidence of TEAEs will be tabulated by system organ class and preferred term and by severity and relationship to treatment. Summaries of TEAEs leading to investigational product discontinuation and SAEs will be provided.

The incidence of TEAEs and SAEs will be tabulated by system organ class and preferred term and similarly by severity and relationship to treatment.

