10.2.3. TEAE Analyses

All AE summaries will be restricted to TEAEs. Summaries that are displayed by SOC and PT will be ordered by descending order of incidence of system organ class and preferred term within each system organ class. Summaries of the following types will be presented:

- Overall summary of TEAEs
- Subject incidence of TEAEs and the total number of entries by MedDRA SOC and PT.
- Subject incidence of TEAEs by MedDRA SOC, PT, and highest severity. At each level of subject summarization, a subject is classified according to the highest

severity if the subject reported 1 or more events. AEs with missing severity will be considered severe for this summary.

- Subject incidence of TEAEs by MedDRA SOC, PT, and closest relationship to investigational product (Related/Not Related). Related AEs are those with relationships reported as “Definite,” “Probable,” or “Possible,” and unrelated AEs are those with relationships reported as “Unlikely” or “Not Related.” At each level of subject summarization, a subject is classified according to the closest relationship if the subject reported 1 or more events. AEs with a missing relationship will be considered related for this summary.
- Subject incidence of serious TEAEs and the total number of entries by MedDRA SOC and PT.
- Subject incidence of TEAEs leading to investigational product withdrawal or study discontinuation by MedDRA SOC and PT. This is a subset of the AEs where Action Taken with Study Treatment is checked as “Drug Withdrawn” or where “Subject Discontinued from Study” is checked.

The following listings will be presented by subject:

- All adverse events
- Serious adverse events (a subset of the AEs where serious is marked as “Yes”).
- Severe adverse events (a subset of AEs where severity is marked as “Severe”).
- Related adverse events (a subset of the AEs where relationship marked as “Definite,” “Probable,” or “Possible”).
- Adverse events leading to Study Drug Withdrawal or Study Discontinuation (a subset of the AEs where Action Taken with Study Treatment is checked as “Drug Withdrawn” or where “Subject Discontinued from Study” is checked).
- Adverse events leading to death.

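### SAP 10.2.3 plans no table of TEAEs leading to interruption or reduced dosing frequency, and pools drug withdrawal with study discontinuation

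*SAP*

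**What the plan says.** Protocol 6.1 makes tolerability part of the main question: "The primary objective is to assess the long-term safety and tolerability of the OCA + BZF FDC tablet in subjects with PBC".

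For a subject who tolerates the tablet poorly, protocol 7.6 states: "In the event of tolerability issues such as pruritus, the dosing frequency may be decreased at the discretion of the Investigator". Section 14.1.3.1 adds drug holidays and, for pruritus, "Less frequent dosing of investigational product (e.g., on alternate days) may be administered". It also requires capture: "Details of drug holidays and/or nondaily dosing regimens should be recorded in the eCRF". Table 4 (7.4.2) and 7.4.4.3 require interruption on liver or CK triggers, and Table 4 allows a restart under conditions.

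On reporting, protocol 15.3.1 states: "Summaries of TEAEs leading to investigational product discontinuation and SAEs will be provided". SAP 10.2.3 instead plans "Subject incidence of TEAEs leading to investigational product withdrawal or study discontinuation by MedDRA SOC and PT", and defines it as follows: "This is a subset of the AEs where Action Taken with Study Treatment is checked as" 'Drug Withdrawn', or where the study-discontinuation box is checked. The matching listing has the same limits. SAP 11 states that the planned analyses do not deviate from the protocol.

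**The concern.** In this trial, interruption and less frequent dosing are meant to keep subjects on drug who might otherwise stop. A table limited to withdrawal therefore cannot describe tolerability alone. It treats an event that led to repeated holidays or alternate-day dosing like one that needed no action.

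The steps short of stopping bear directly on three of the four AESIs in SAP 10.2.4: pruritus (holidays, alternate days), hepatic injury (Table 4 liver triggers) and myalgia (CK trigger and myopathy monitoring).

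Pooling is a second, smaller matter. The protocol asks subjects who stop the tablet to keep attending to Month 60, so stopping drug and leaving the study are different outcomes. A pooled table by SOC and PT cannot tell them apart.

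**Working it through.** The plan has no figure to reproduce: about 133 subjects is the rollover number, with no hypothesis or power calculation. The check sets the sections side by side, tests whether SAP 10.1 fills the gap, and then illustrates the size.

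**Step 1. Protocol action against planned output**

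| Action | Protocol | Reaches the SAP 10.2.3 action-taken table? |
|---|---|---|
| Related AE of Grade 3 or above: discontinue | 8.4.1.1 | Yes |
| Table 5 event: permanent discontinuation | 7.4.3, 8.4.1 | Yes, if recorded as an AE |
| Drug holiday over 30 days: permanent discontinuation | 14.1.3.1 | Yes |
| Drug holiday of 30 days or less | 14.1.3.1 | No |
| Less frequent or alternate-day dosing | 7.6, 14.1.3.1 | No |
| Liver or CK trigger: interruption with restart | Table 4, 7.4.4.3 | No |

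The AESI sections add only crude incidence of TEAEs and SAEs. The rows of the overall TEAE summary are not listed, so an interruption row cannot be assumed.

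**Step 2. Does SAP 10.1 fill the gap?** Its formulas are:

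- exposure = (last dose date − first dose date + 1) − total interruption
- one interruption = restart date − discontinuation date + 1
- compliance = tablets consumed / tablets expected × 100

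Take a subject with 180 days from first to last dose.

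- *Alternate days for 60 of the 180 days.* Protocol 14.1.3.1 says that nondaily dosing is not a drug holiday, so nothing is subtracted and exposure stays at 180 days. Tablets taken are 180 − 30 = 150. Compliance is 150/180 = 83.3% if 'expected' means daily, and 150/150 = 100% if it means as prescribed. The SAP does not say which.
- *A 14-day holiday, first missed dose on day 61, restart on day 75.* The interruption is 75 − 61 + 1 = 15 days, exposure is 180 − 15 = 165 days, and tablets taken are 180 − 14 = 166.

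SAP 10.1 also counts subjects with at least one decrease in dose. For a single-strength tablet that term is undefined, so it is unclear whether alternate-day dosing qualifies. No count of interrupted subjects is stated, and nothing in SAP 10.1 ties a dosing change to an event.

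**Step 3. Illustrative size.** All rates here are assumptions: N = 133, non-overlapping groups, exact (Clopper-Pearson) 95% intervals for the end cases. Assume that 5–10% withdraw for an AE (0.05 × 133 ≈ 7; 0.10 × 133 ≈ 13) and a further 5–20% only interrupt or cut frequency (≈ 7 to 0.20 × 133 ≈ 27).

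| Withdraw | Interrupt or cut only | Planned table | Any AE-driven dosing change |
|---|---|---|---|
| 7 | 7 | 7/133 = 5.3% (2.1–10.5) | 14/133 = 10.5% (5.9–17.0) |
| 7 | 27 | 7/133 = 5.3% | 34/133 = 25.6% |
| 13 | 7 | 13/133 = 9.8% | 20/133 = 15.0% |
| 13 | 27 | 13/133 = 9.8% (5.3–16.1) | 40/133 = 30.1% (22.4–38.6) |

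The two right-hand columns measure different things. Their gap is the information left untabulated under the assumed rates. It is not a bias in the planned table.

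**Step 4. Pooling.** Protocol 15.3.1 names TEAEs leading to investigational product discontinuation. SAP 10.2.3 adds study discontinuation to the same table, while SAP 11 declares no deviation.

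**The case against.** The strongest reply is that no event is lost. Every TEAE that prompts a holiday or alternate-day dosing is counted in the SOC/PT, severity and relationship tables, in the AESI tables where it applies, and in the listing of all AEs. The withdrawal table is labelled as such and reports withdrawals correctly. This stands. A reader might infer that adverse-event incidence, or tolerability as a whole, is understated; the documents do not support that.

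A reader might also infer that permanent stopping always follows the milder steps. It does not: related Grade 3 events and Table 5 events go straight to discontinuation, and holidays over 30 days become discontinuations. What goes untabulated is therefore mainly milder or unrelated events, shorter holidays, and laboratory interruptions that end in a restart.

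Four further points carry some weight:

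- SAP 6 tabulates study discontinuation and drug discontinuation separately with reasons, which partly answers the pooling point, though not by SOC and PT.
- Laboratory triggers also show up in the SAP 10.3 shift tables and Hy's law summary, and potential hepatic injury is adjudicated.
- Entry criteria favour subjects who tolerate treatment: they must be actively taking parent-study product, and recent severe pruritus is excluded. Actual rates could be low.
- The protocol itself promises no table of interruptions, so on that item the SAP omits nothing promised.

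None of these shows which events changed dosing, or in how many subjects.

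**Conclusion.** The gap is real but limited. The plan reports how often adverse events occur and how often they end treatment or participation. It has no pre-specified result for how often they lead to interruption or less frequent dosing, although the protocol relies on those measures and tolerability is in the primary objective. SAP 10.1 shows part of the change in intake but not its cause, and some of its terms are undefined for this regimen.

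The size cannot be taken from the documents. Under the assumed rates, between 7 and 27 of 133 subjects (5.3% to 20.3%) would have an event-driven dosing change that no adverse-event table shows. This is a reporting gap worth closing before the SAP is final; it does not bias any planned estimate. The pooled table is a small departure from protocol 15.3.1 that SAP 11 does not acknowledge.

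**What to change.** 1. **SAP 10.2.3, additions.** Add subject incidence of TEAEs leading to investigational product interruption, and of TEAEs leading to reduced dosing frequency, by SOC and PT and for each AESI. Use the action-taken field and the eCRF records of holidays and nondaily dosing. First confirm that these records can be linked to individual events; the documents show only the withdrawal and study-discontinuation checks, and the eCRF is not among them.
2. **SAP 10.2.3, split.** Separate the pooled table into TEAEs leading to permanent drug discontinuation, as protocol 15.3.1 names, and TEAEs leading to study discontinuation. Otherwise record the pooling in SAP 11.
3. **SAP 10.1.** Add the number and percentage of subjects interrupted. State whether nondaily dosing counts as a decrease in dose, and how expected tablets are set during it.
4. **Reconcile two protocol passages.** Section 14.1.3.1 turns a drug holiday of more than 30 days into permanent discontinuation, whereas the Table 4 footnote allows restart only after a minimum of 30 days. The documents should say how the two fit together, because this affects which events are coded 'Drug Withdrawn'.

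The cost is SAP wording and a few extra descriptive tables, with no change to study conduct if the link in item 1 exists. If it does not, a data-capture change is needed for the additions in item 1.

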10.2.4. Adverse Events of Special Interest (AESI)

The AESIs include pruritus, hepatic injury, myalgia and renal impairment.

10.2.4.1. Pruritus

Pruritus is both the most common symptom of PBC and was the most frequently reported AE in the Phase 2 PBC studies for OCA. Accordingly, pruritus is considered an AE of special interest.

Treatment-emergent pruritus, defined as any preferred term including “Prur,” will be summarized separately by the MedDRA SOC, treatment group, and PT as a subset of all TEAEs. Summaries will include a summary of the crude incidence of Pruritus TEAEs and SAEs by system organ class and preferred terms. Hepatic Injury

Hepatic injury is defined as events included in the Hepatic Disorder Standardized MedDRA query (SMQ), excluding the following sub-SMQs: alcohol related, congenital, familial, neonatal and genetic disorders of the liver; liver infections; and pregnancy-related hepatic injury. Summaries will include a summary of the crude incidence of hepatic disorder TEAEs and SAEs by system organ class and preferred terms.

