5.6.2. Risks

The known and potential risks of OCA and BZF are described in the FDC Investigator's Brochure and are summarized in Table 1 and Table 2, respectively.

Table 1: Known and Potential Risks of OCA

OCA
Hepatic Adverse Events
Hepatic failure, sometimes fatal or resulting in liver transplant, has been reported with OCA treatment in PBC patients with decompensated cirrhosis.
Some of these cases occurred in patients with decompensated cirrhosis when they were treated with higher than the recommended dosage for that patient population; however, cases of hepatic decompensation and failure have continued to be reported in patients with decompensated cirrhosis even when they received the recommended dosage. Per the CCDS v5.0, Ocaliva is contraindicated in patients with PBC with decompensated cirrhosis (e.g., Child-Pugh Class B or C) or a prior decompensation event and in patients with complete biliary obstruction. Ocaliva is also contraindicated in patients with compensated cirrhosis with evidence of portal hypertension (e.g. ascites, gastroesophageal varices, persistent thrombocytopenia).
A dose-response relationship was observed for the occurrence of hepatic adverse reactions including jaundice, worsening ascites and primary biliary cholangitis flares with dosages of OCA of 10 mg once daily to 50 mg once daily (up to 5-times the highest recommended dosage), as early as one month after starting treatment with OCA in two 3-month placebo-controlled clinical trials in patients with primarily early stage PBC.

In a pooled analysis of three placebo-controlled clinical trials, in patients with primarily early stage PBC disease, the exposure-adjusted incidence rates for all serious and otherwise clinically significant hepatic adverse reactions, and isolated elevations in liver biochemical tests, per 100 PEY were: 5.2 in the OCA 10 mg group (highest recommended dosage), 19.8 in the OCA 25 mg group (2.5-times the highest recommended dosage) and 54.5 in the OCA 50 mg group (5-times the highest recommended dosage) compared to 2.4 in the placebo group.

Pruritus

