15.2. Determination of Sample Size

This is an estimation study with no formal hypothesis to be tested. Therefore, sample size is strictly based on number of subjects being captured from studies 747-213 and 747-214, or other Sponsor studies. The sample size in this study is not calculated based on statistical consideration.

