2. STUDY OBJECTIVES AND HYPOTHESES

2.1. Study Objectives

2.1.1. Primary Objective

[figure not shown]
The primary objective is to assess the long-term safety and tolerability of the Obeticholic Acid (OCA) + Bezafibrate (BZF) Full Dose Combination (FDC) tablet in subjects with Primary Biliary Cholangitis (PBC).

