3. SUMMARY OF STUDY DESIGN

3.1. Overall Study Design

This Phase 3, open-label, LTSE study will evaluate the safety, tolerability, and efficacy of the OCA + BZF FDC tablet (OCA 5 mg + BZF 400 mg SR) in approximately 133 subjects with PBC for up to 60 months (5 years).

- For subjects from Study 747-213 or Study 747-214 who continue to meet that protocol's requirements, they will transition into Study 977-311 once the study is active at their respective sites. The time subjects have spent in the LTSE phases in

their respective studies, 747-213 or 747-214, will not count toward the 60 months in Study 977-311.

- Eligible subjects from other Sponsor studies may also transition to Study 977-311.

[figure not shown]
All subjects will transition in Study 977-311 to the OCA + BZF FDC tablet (OCA 5 mg + BZF 400 mg SR) and will receive investigational product once daily at the same time (AM dosing is preferred to align with all study visits) starting on Day 2. All subjects should continue their pre-study dose of UDCA throughout study participation.

After Day 1, Day 2, Month 1, Month 3, Month 6, and Month 12 visits, subsequent in-clinic study visits will occur every 6 months for the assessment of safety, tolerability, efficacy, PK, and PD.

The study design diagram is presented in [Figure 1: Study Design Schematic](#).

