3.4. Sample Size Determination

The sample size in this study is not calculated based on statistical consideration.

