9.2. Exploratory Endpoints

– MELD score ≥ 15

- Time to first occurrence of each individual component of the composite event endpoint.

All continuous and categorical additional efficacy endpoints will be summarized using descriptive statistics at baseline and at each scheduled post-baseline visit. No statistical inference will be done on those endpoints.

Kaplan-Meier (KM) estimates will be calculated for all time to event endpoints. The quartiles, including the median time-to-event and their respective 2-sided 95% CIs, will be presented. KM estimates will be plotted as a “survival curve”.

For the additional endpoints, data collected after the intercurrent events, such as the use of prohibited medications, and data collected after treatment discontinuation will be included.

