10.1. Exposure to Study Treatment

The extent of exposure will be summarized using descriptive statistics.

Duration of exposure (days) to investigational product will be calculated as follows:

- Exposure to investigational product = [(Date of last investigational product dose – Date of 1st investigational product dose) + 1] – Total duration of temporary investigational product discontinuation

The duration of each incidence of temporary investigational product discontinuation will be calculated as follows:

- Duration of temporary discontinuation of investigational product = (Date of restart of investigational product – Date of temporary discontinuation of investigational product) + 1.

The total duration of temporary investigational product discontinuation is the sum duration of temporary discontinuation of investigational product over each incidence of discontinuation.

Total subject exposure to investigational product will be calculated by adding the doses taken by a subject during the study and will be summarized using descriptive statistics.

A summary of subjects who had an increase in dose and who had a decrease in dose at least once during the study will be provided in terms of frequency count (n) and percentages (%).

Subject's overall compliance (%) with investigational product will be calculated as follows:

- $\text{number of tablets consumed during study} / \text{number of tablets expected to be consumed during study} * 100$

where

- $\text{number of tablets consumed during study} = \text{number of tablets dispensed} - \text{number of tablets returned}$

Subject compliance with investigational product will be summarized using descriptive statistics. Percent compliance will be summarized separately for subjects who completed the study versus those who withdrew early so as to distinguish between those subjects who were compliant throughout the entirety of the study versus those who were compliant until they withdrew from the study.

All exposure data will be presented in a by subject data listing.

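### Long-term safety is to be reported as crude incidence without person-time rates or confidence intervals, and time-to-event outcomes without risk estimates at set times

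*SAP*

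**What the plan says.** SAP 2.1.1 states the aim: "The primary objective is to assess the long-term safety and tolerability of the" fixed-dose tablet. Protocol 15.2 adds that "This is an estimation study with no formal hypothesis to be tested". About 133 subjects in a single arm may be treated for up to 60 months.

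**Adverse events.** SAP 10.2.3 plans subject incidence and number of entries by system organ class and preferred term. SAP 10.2.4 plans crude incidence for the events of special interest, for example "Summaries will include a summary of the crude incidence of Pruritus TEAEs and SAEs by system organ class and preferred terms". Safety analyses use everyone who took at least one dose (SAP 4.1 and 10). All adverse event summaries are restricted to treatment-emergent events (SAP 10.2.3), and an event starting more than 30 days after the last dose is not one (SAP 10.2.1). SAP 10.1 derives exposure for each subject but does not link it to events.

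**Reference data.** Protocol 5.6.2, Table 1 reports "the exposure-adjusted incidence rates for all serious and otherwise clinically significant hepatic adverse reactions" and isolated liver-test elevations per 100 patient exposure years: 5.2 on OCA 10 mg and 2.4 on placebo.

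**Exploratory time-to-event endpoints.** SAP 9.2 calculates and plots Kaplan-Meier estimates. On numerical output it says: "The quartiles, including the median time-to-event and their respective 2-sided 95% CIs, will be presented".

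**Treatment gaps.** SAP 10.1 sets each gap to ("Date of restart of investigational product – Date of temporary discontinuation of investigational product) + 1").

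**The concern.** A crude percentage depends on how long subjects were observed as well as on their risk. Observation on treatment will be unequal here. The investigational product must be stopped for the events in Protocol Table 5 and for related events of Grade 3 or above (Protocol 8.4.1), and the pruritus guidance adds drug holidays of more than 30 days (14.1.3.1). Calendar time adds to this: the synopsis gives first enrollment in July 2024 and estimated last completion in Q2 2029, while 60 months from July 2024 is July 2029.

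A subject who stops early adds almost no further time in which an event could count, yet remains in the denominator. The reported percentage then falls below the on-treatment risk, and the table shows neither by how much nor how precise the figure is. In an estimation study whose primary objective is long-term safety, the estimate and its precision are the main product. The planned tables also could not be set directly beside the protocol's own hepatic rates, which are per 100 patient-years.

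For the clinical outcomes, a quartile or median that is not reached is reported as not estimable, which gives no number for risk at any time.

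**Working it through.** **Inputs**
- N is about 133. There is no planning figure to reproduce: "The sample size in this study is not calculated based on statistical consideration" (SAP 3.4).
- Horizon T = 5 years for every subject.
- Event rate L: 5.2 and 2.4 per 100 patient-years (Protocol 5.6.2), assumed constant. They come from other regimens and are reference values, not predictions.
- Discontinuation rate d: not stated in either document. Assumed 0, 10% and 20% per year, unrelated to the event.

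**1. Crude incidence against five-year risk**

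True five-year on-treatment risk = 1 − exp(−5L). Expected crude proportion = L/(L+d) × (1 − exp(−5(L+d))).

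For L = 0.052 and d = 0.10: (0.052/0.152) × (1 − exp(−0.76)) = 0.342 × 0.532 = 18.2%.

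| L per 100 PY | True risk | Crude, d = 0 | Crude, d = 10% | Crude, d = 20% |
|---|---|---|---|---|
| 5.2 | 22.9% | 22.9% | 18.2% | 14.8% |
| 2.4 | 11.3% | 11.3% | 8.9% | 7.2% |

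The formula ends the counting window at the last dose. The 30-day extension adds about P(stop before event) × L × 30/365.25. At L = 0.052 and d = 0.10 this is 0.350 × 0.052 × 0.082 = 0.0015, or 0.15 percentage points, which does not change the picture.

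**2. Event rate needed to reach the quartiles by 5 years**

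Rate = −ln(1 − q)/5.
- 25%: 0.2877/5 = 5.75 per 100 PY
- 50%: 0.6931/5 = 13.9 per 100 PY
- 75%: 1.3863/5 = 27.7 per 100 PY

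Chance of reaching them in 4,000 simulated Kaplan-Meier curves per scenario (N = 133, d = 0 or 10% per year):

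| Rate per 100 PY | Lower quartile reached | Median reached |
|---|---|---|
| 2.4 | 0% | 0% |
| 4.0 | 2 to 4% | 0% |
| 5.2 | 26 to 30% | 0% |
| 5.75 | 48% | 0% |
| 8.0 | 96 to 97% | 0% |
| 12 | 100% | 13 to 17% |

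**3. What rates and intervals would add**

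For L = 0.052 and d = 0.10, person-time to first event, stop or 5 years is 133 × 0.532/0.152 = 466 PY, with 133 × 0.182 = about 24 events. The exact Poisson limits give about 3.3 to 7.7 per 100 PY. A 60-month Kaplan-Meier risk of 22.9% would have a half-width of about 8.1 points. With no events in 133 subjects, the exact two-sided 95% upper limit is 1 − 0.025^(1/133) = 2.7%.

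**4. Gap formula**

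First missed dose 10 January, restart 11 January: one day is missed.
- Stop date taken as first missed dose: 11 − 10 + 1 = 2 days, 1 too many.
- Stop date taken as last dose (9 January): 11 − 9 + 1 = 3 days, 2 too many.

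Assuming five gaps per subject, the excess is 133 × 5 = 665 days (1.8 PY) at one day per gap and 1,330 days (3.6 PY) at two. Against 466 PY that is 0.4% to 0.8%.

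**The case against.** **The survival curve is already planned.** From the quartile sentence a reader might infer that the plan cannot state long-term risk at all. The adjoining sentences in SAP 9.2 do not support that: the estimates are calculated and plotted, so a 60-month value can be read from the curve. What is missing is a named time point with its interval and the number at risk.

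**The quartiles might be reached.** A reader might infer that they certainly will not be. The visible text gives no expected rate for the composite, and most of its components are redacted. At 5.2 per 100 PY the lower quartile would still be reached 26 to 30% of the time. That rate describes hepatic adverse reactions and not the time-to-event endpoints, so it cannot date their quartiles.

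**Rates can be approximated from planned tables.** Total entries and mean exposure are both reported, so comparison with the reference rates is not impossible. This stands in part. It yields an approximate event rate, but not a first-event rate, a by-year rate or an interval.

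**The hazard may not be constant.** Entrants already take parent-study product, and Protocol Table 1 describes early onset of hepatic reactions and severe pruritus. This is fair, and it favors rates by study year over a single overall rate.

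**Competing events.** A reader might infer that Kaplan-Meier will overstate component risks by censoring death or transplant. The visible text states no censoring rule, so this can only be a request to specify one.

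**Efficacy intervals.** SAP 9 mentions 95% intervals for all efficacy analyses, while SAP 9.1 says no inference will be done. Whether response rates get intervals is unclear, so this point is confined to safety and the time-to-event endpoints.

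**Conclusion.** The point holds in this form: the SAP does not prespecify an exposure-based or time-based estimate of risk, with its precision, for the study's primary objective.

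The size depends on how many subjects stop. At 5.2 per 100 PY, crude incidence would fall 4.7 points short of the five-year risk at 10% per year discontinuation (22.9 − 18.2) and 8.1 points short at 20% (22.9 − 14.8). With nobody stopping and full follow-up there is no shortfall. These figures assume a constant rate, discontinuation unrelated to the event, and the SAP's 30-day limit. The treatment-emergent definition in Protocol 14.1.1.3 has no such limit, and under it the shortfall would be smaller for subjects who stop but stay in follow-up.

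For the time-to-event endpoints, the median is unlikely to be reached at rates like those in the documents and the lower quartile may not be. The gap error is real under either reading of the stop date, but small; it shortens exposure and so would slightly raise any rate computed from it.

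No figure in the documents is shown to be wrong. The change should be made before the SAP is finalized, which Protocol 15 requires before any study snapshot.

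**What to change.** 1. **SAP 10.2.3 and 10.2.4:** add incidence per 100 patient-years with exact 95% confidence intervals for treatment-emergent events, serious events, events of special interest and discontinuations, overall and by study year. Define person-time to match the counting window, including the 30 days after the last dose. Keep the crude percentages alongside.
2. **SAP 9.2:** add Kaplan-Meier estimates at Months 12, 24, 36, 48 and 60 with 95% intervals and numbers at risk. State the censoring rule, and use cumulative incidence where death or transplant is a competing event for a component. Numbers at risk matter most at Month 60, because on the synopsis dates few or no subjects may reach it.
3. **SAP 10.1:** define gap length as restart date minus date of first missed dose, without the added day.

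The cost is SAP text and a few table columns. Event and exposure dates are already collected, so no new data or visits are needed.
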